1.3 Schema

The general study design is summarized in Figure 1.

Figure 1 **Study Design**

LOH loss of heterozygosity; iHRD integrated homologous recombination deficiency

2. INTRODUCTION

2.1 Background and Study Rationale

METASTATIC CASTRATION RESISTANT PROSTATE CANCER:

Prostate cancer remains the second leading cause of cancer death among American men despite significant treatment advances in the past decade.³ Advanced prostate cancer is an androgen-dependent malignancy, and the mainstay of treatment is androgen deprivation therapy and other hormonally targeted agents. However, resistance to these therapies inevitably develop, leading to the late and inevitably fatal disease state known as metastatic castration resistant prostate cancer (mCRPC). Resistance is thought to be conferred by various mechanisms, including increased intratumoral steroidogenesis, increased androgen receptor expression, and constitutively active androgen receptor splice variants. In addition there are several somatic genomic alterations that are associated with aggressive disease, including *TP53* mutations or deletions, *PTEN* loss, and defects in DNA-repair genes.⁴ While recent approvals have expanded the treatment toolbox for patients with certain genetic alterations, the continued lethality of this disease highlights the need for additional therapeutic options.

HOMOLOGOUS RECOMBINATION DEFICIENCY AND RESPONSE TO PARP INHIBITORS:

Inactivating mutations in homologous recombination (HR) genes have been associated with improved responses to PARP inhibitors (PARPi) in men with mCRPC, likely through the induction of synthetic lethality. The TOPARP-A trial observed a response rate to the PARPi olaparib of 88% in men with homozygous deletions or deleterious mutations in DNA-repair genes compared to 6% in men without these alterations.⁵ Further work has shown that response rates to PARP inhibitors vary dramatically depending on the affected gene.^{6,7} 83.3% of men with *BRCA 1/2* alterations responded to olaparib (50% decline in PSA or RECIST 1.1 objective response) in the TOPARP-B trial compared to 10.5% with ATM mutations and 0% with *CDK12* mutations.⁷ The finding of heterogeneous clinical outcomes based on affected gene has been recapitulated in both the TRITON2 and PROfound studies.^{2,6} This variability in response underscores the problem with relying on 3-15 gene panels to define homologous recombination deficiency (HRD) for the purpose of selecting patients for treatment with PARPi. Furthermore, there is also a subset of patients without known deleterious mutations who still respond to treatment with a PARPi.⁵ Taken together, these observations suggest that defects in DNA-repair genes are an imperfect biomarker to predict response to PARP inhibition and highlight the need for development of novel predictive strategies.

Differences in response to PARPi by affected gene may partially be explained by the fact that not all genes have the same biologic significance in terms of their role in mediating homologous recombination repair. In addition, next generation sequencing (NGS) assays looking for mutation defects in specific genes will miss epigenetic and cryptic events that result in HRD. Therefore, functional measures of HRD should provide a more reliable means for selecting patients who would benefit from treatment with a PARP inhibitor.

PREDICTING HOMOLOGOUS RECOMBINATION DEFICIENCY:

Homologous recombination repair (HRR) is a key pathway involved in resolving double-stranded DNA (dsDNA) breaks. HRR utilizes the undamaged sister chromatid as a template in order to produce error-free repair of the dsDNA damage.⁸ When functional defects occur in this pathway by germline and/or somatic events, characteristic genome wide alterations occur, which result in predictable tumor signatures that can be called using bioinformatic tools. This HR deficiency signature calling has the potential to complement existing genomic biomarkers being developed to identify those likely to benefit from PARPi treatment.⁹

Several scores have been developed in an attempt to identify functional loss of HR activity, however, there are important limitations to the most widely used approaches¹⁰⁻¹³. An LOH-based score has been validated in epithelial ovarian cancer to strongly associate with functional defects in *BRCA1* and *BRCA2* as well as methylation of the promoter region of *RAD51C*, another gene in the HR pathway.¹⁰ Although this score may capture an additional subset of patients who have HRD tumors than those captured by NGS alone, it is impacted by tumor ploidy and cellularity and thus may lack specificity. The COSMIC 3 signature has been developed based on unique genomic alterations associated with the loss of *BRCA1/BRCA2*.^{14,15} However, this signature does not appear to reliably discriminate between responder/non-responders to olaparib (Figure 2).

To address these shortcomings, our group has developed an integrated approach to calling HRD signatures (iHRD - integrated Homologous Recombination Deficiency), with the goal of more reliably defining prostate cancer tumors that will be sensitive to DNA damaging therapeutics such as PARPi. This signature is a multiparametric classification that was defined using 418 patient samples from the Stand Up 2 Cancer (SU2C) repository and was subsequently validated on a set of cases from our UW rapid autopsy program. iHRD was more closely associated with improved clinical outcomes in patients receiving olaparib on the TOPARP-B study (Figure 2)⁵. Importantly, iHRD also allows us to identify *11-12% of mCRPC patients who do not have mutations in HR genes but who we would predict to have functional loss of HR and therefore stand to benefit from PARP inhibition* (Figure 3).

[figure not shown]

Figure 2. iHRD accurately predicts time on olaparib treatment. Data from 22 clinical cases of men with mutations in HRR genes treated with olaparib was re-analyzed, with time on olaparib treatment stratified by HRD mutational status, COSMIC3 signature and iHRD status. iHRD was more closely associated with time on olaparib than other approaches. iHRD correlated with time on olaparib treatment (top). Kaplan-Meier estimates showed a significant association between time on olaparib treatment and iHRD positivity; however, neither HR-biallelic loss nor COSMIC3 signature was associated with longer time on treatment.

[figure not shown]

Figure 3. iHRD distribution across HR mutant subgroups. Spectrum of iHRD distribution across homologous recombination (HR) and putative HR associated gene mutant subgroups. Bi-allelic BRCA1, BRCA2, ATM, and PALB2 as biomarkers would potentially miss 65 of 107 iHRD+ mCRPC.

OLAPARIB BACKGROUND

Investigators should be familiar with the current olaparib (AZD2281) Investigator Brochure (IB).

Olaparib (AZD2281, KU-0059436) is a potent Polyadenosine 5'diphosphoribose [poly (ADP ribose)] polymerization (PARP) inhibitor (PARP-1, -2 and -3) that is being developed as an oral therapy, both as a monotherapy (including maintenance) and for combination with chemotherapy and other anti-cancer agents.

PARP inhibition is a novel approach to targeting tumors with deficiencies in DNA repair mechanisms. PARP enzymes are essential for repairing DNA single strand breaks (SSBs). Inhibiting PARPs leads to the persistence of SSBs, which are then converted to the more serious DNA double strand breaks (DSBs) during the process of DNA replication. During the process of cell division, DSBs can be efficiently repaired in normal cells by homologous recombination repair (HR). Tumors with HR deficiencies (HRD), such as prostate cancers in patients with *BRCA1/2* mutations, cannot accurately repair the DNA damage, which may become lethal to cells as it accumulates. In such tumor types, olaparib may offer a potentially efficacious and less toxic cancer treatment compared with currently available chemotherapy regimens.

Olaparib is currently FDA approved for men with metastatic castration resistant prostate cancer who have germline or somatic defects in any one of 14 HRR genes and who have progressed following treatment with enzalutamide or abiraterone. This approval was granted on the basis of the PROfound study – a Phase III randomized, open-label, multi-center trial¹⁶. Patients were eligible to enroll if they had mCRPC and had previously received either enzalutamide or

CLINICAL STUDY PROTOCOL - V3.0, OCTOBER 21, 2022

Olaparib - ESR-20-20693

CONFIDENTIAL AND PROPRIETARY

abiraterone and who had HRR gene alterations. Men received either olaparib 300mg twice daily or investigator's choice of either abiraterone or enzalutamide. The primary endpoint was progression free survival (PFS) in the group with *BRCA1*, *BRCA2* and/or *ATM* mutations (Cohort A). A second cohort consisted of patients with mutations in other HR repair-associated genes (Cohort B). Secondary endpoints were analyzed in a hierarchical fashion to control for trial-wide type 1 error associated with multiple testing, which occurred in the following order: objective response rate (Cohort A), PFS (combined Cohorts A and B), time to pain progression (Cohort A), and overall survival (Cohort A).

The primary endpoint of PROfound was met, with a PFS of 7.4 months vs. 3.6 months ($P<0.001$) in the olaparib vs. control groups for Cohort A. Secondary endpoints also favored the olaparib group, with an objective response rate in Cohort A of 33% vs. 2% in control group ($P<0.001$), median PFS of 5.8 months vs. 3.5 months for combined Cohorts A and B ($P<0.001$), median overall survival of 18.5 months vs. 15.1 months for Cohort A ($P=0.02$) and median overall survival of 17.5 months vs. 14.3 months for combined Cohorts A and B ($P=0.0063$). These results led the FDA to approve olaparib for a broad group of mCRPC patients with somatic or germline alterations in *BRCA1*, *BRCA2* or any of 12 additional HR repair pathway genes.

It should be noted that data supporting the use of olaparib in patients with non-*BRCA* mutations is sparse. There was no clear difference in PFS observed in either *ATM* ($N=86$) or *CDK12*-mutated ($N=89$) (Figure 2B and Supplemental Figure S5) patients enrolled on PROfound. In addition, the reported PSA and radiographic response rates for *ATM* (5.3% and 8.3%, respectively) and *CDK12*-mutated mCRPC (0% for both) was also low in TOPARP-B⁷. These results highlight the need for refinement of HRD biomarkers.

HYPOTHESIS:

Based on these observations, we hypothesize that iHRD signature analysis will allow us to identify more men who are likely to benefit from PARP inhibitors, including those (11-12% of mCRPC population) who are otherwise excluded from clinical trials evaluating these agents. We therefore plan to conduct a Phase II study to evaluate the utility of using iHRD signature analysis to select patients for treatment with olaparib.

2.2 Benefit/Risk Assessment

Olaparib is an FDA approved therapy for men with mCRPC and mutations in genes associated with homologous recombination repair based on improved progression free survival compared to novel hormonal agents (i.e. abiraterone or enzalutamide)¹⁷. This trial will include men with mCRPC and evidence of HRD based on a novel integrated genomic signature (iHRD). Based on the aforementioned rationale, we anticipate that olaparib will be effective in this patient population. One benefit of this study is access to a potentially efficacious antineoplastic medication that would not otherwise be available for a subset of men with mCRPC. Further, men in this study will have already progressed on at least one approved therapy for mCRPC, and effective treatment options remain somewhat limited for this patient population.

Risks of participating in this study are the known toxicities of olaparib, including hematologic toxicities, infections associated with myelosuppression, gastrointestinal toxicity, venous

thromboembolic events and risk of secondary leukemias/myelodysplastic syndrome¹⁷. For information on all identified and potential risks with olaparib refer to the current version of the IB. Overall, the investigators feel that the benefits of participating in this study outweigh the risks of participation.

3. OBJECTIVES AND ENDPOINTS

3.1 PRIMARY OBJECTIVE:

Determine the percent of patients achieving a $\geq 50\%$ reduction in PSA (PSA50 response) following at least 12 weeks of treatment with olaparib 300mg twice daily in men with metastatic castration-resistant prostate cancer (mCRPC) who are iHRD+ and who have progressed on a second generation hormonal agent (e.g. abiraterone or enzalutamide).

3.2 SECONDARY OBJECTIVES:

6. Determine the percent of iHRD+ mCRPC patients achieving radiographic response per RECIST 1.1 criteria following treatment with olaparib.
7. Determine the radiographic progression free survival (PFS) in iHRD+ mCRPC patients treated with olaparib.
8. Determine the PSA PFS according to PCWG3 criteria in iHRD+ mCRPC patients treated with olaparib.
9. Determine the overall survival in iHRD+ mCRPC patients treated with olaparib.
10. Assess the incidence and severity of adverse events according to the National Cancer Institute- Common Terminology Criteria for Adverse Events (CTCAE) version 5.0.

3.3 EXPLORATORY OBJECTIVES:

Correlative work will be conducted to assess differences in clinical outcomes in those with vs. without iHRD positivity. This work will also allow us to further understand the biology underlying these differences. Serial blood samples and metastatic tissue will be obtained at baseline and upon progression. Examples of studies to be conducted may include, but are not limited to:

1. Evaluate for differences in radiographic/PSA response and PFS in patients who are iHRD+ compared to patients who are iHRD-.
2. Evaluate for differences in radiographic/PSA response and PFS by specific HR gene involvement.

3. Compare iHRD signature to other functional methods of predicting HRD including large scale state transition (LST) score and COSMIC signature 3/8 status, Telomeric allelic imbalance (TAI) score, and presence of underlying HRR mutation.
4. Optimize iHRD signature based on the results of this trial and develop a pipeline for calling iHRD from targeted exome panels.
5. Conduct transcript profiling studies on metastatic tissue.

3.4 PRIMARY ENDPOINT:

Lowest on-treatment PSA, following at least 12 weeks of olaparib in men with mCRPC who are iHRD+

3.5 SECONDARY ENDPOINTS:

The following endpoints will be assessed in men with iHRD+ mCRPC treated with olaparib:

1. Radiographic response rate per RECIST 1.1 criteria
2. Radiographic progression free survival (PFS)
3. PSA PFS according to PCWG3 criteria
4. Overall survival
5. Incidence and severity of adverse events according to the National Cancer Institute-Common Terminology Criteria for Adverse Events (CTCAE) version 4.0.

4. STUDY DESIGN

4.1 Overall Design

This will be a single arm, Phase II study designed to evaluate the clinical activity of olaparib in mCRPC patients with evidence of HRR deficiency as determined using iHRD signature analysis. Patients will initially be screened for eligibility on the basis of a loss of heterozygosity (LOH) score optimized for UW OncoPlex, a clinical grade targeted sequencing assay. Eligible LOH score positive subjects will then enroll and receive treatment with olaparib 300 mg by mouth twice daily. One treatment cycle will be defined as 28-days, and consist of continuous daily dosing of olaparib. All patients will then undergo germline and somatic whole exome sequencing (WES) to assess iHRD status. Only those found to be iHRD+ will be used for the purpose of assessing the primary endpoint (i.e. best PSA response). Those patients that are LOH score-positive/iHRD-negative will be allowed to continue on treatment, however, and will be used in assessment of exploratory objectives. All patients will continue on androgen deprivation therapy (ADT) (i.e. surgical or medical castration) and should have a two-week washout from their most recent mCRPC therapy and weaned from steroids prior to enrolment.

PSA will be measured on day 1 of each treatment cycle. Radiographic assessment with bone and CT scans will occur every 12 weeks. The primary endpoint will be lowest on-treatment PSA and primary objective is to determine the PSA50 rate. Patients will be permitted to continue until disease progression by radiographic (per RECIST 1.1), PSA (per PCWG3 criteria) or clinical criteria (e.g. increasing pain), whichever comes first. Prior to completing 3 cycles of treatment, patients should not discontinue treatment for PSA progression alone. Patients will come off study at time of clinical, radiographic, or PSA progression. Secondary objectives will include assessment of radiographic PFS, PSA PFS, overall survival, and adverse events.

For an overview of the study design see Figure 1, Section 1.3. For details on treatments given during the study, see Section 5.5 Treatments Administered.

For details on what is included in the efficacy and safety endpoints, see Section 3 Objectives and Endpoints.

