1.0 PROTOCOL SUMMARY

1.1 Schedule of Activities (SoA)

Table 1 Schedule of Activities

Treatment Cycle	Pre-Screening	Screening	Treatment Cycles ^a					End of Treatment
			Cycle 1 ^g	Cycle 2	Cycle 3	Cycle 4	After Cycle 4	
Cycle Day		Day -30 to 0	Day 1 +/- 7 days	Day 1 +/- 7 days	Day 1 +/- 7 days	Day 1 +/- 7 days	Day 1 +/- 7 days	Within 30 days
Administrative Procedures								
Informed Consent		X						
Inclusion/Exclusion Criteria		X						
Demographics and Medical History		X						
Prior and Concomitant Medication Review		X	X	X	X	X	Q1C	X
Olaparib Dispensation			X	X	X	X	Q1C	
Clinical Assessments								
Review Adverse Events			X	X	X	X	Q1C	X
ECOG Performance Status		X	X	X	X	X	Q1C	X
Vital Signs and Weight		X	X	X	X	X	Q1C	X
Physical Examination ^b		X	X	X	X	X	Q1C	X

EKG		X						
Laboratory Assessments								
LOH Assessment	X ^d							
iHRD Analysis/Whole Exome Sequencing		X						
PSA		X	X			X	Q3C	X
Testosterone Level		X						
CBC with Differential		X	X	X	X	X	Q1C	X
Comprehensive Serum Chemistry Panel		X	X	X	X	X	Q1C	X
PT/INR and PTT		X						
Urinalysis		X						
Correlative Studies Blood Collection ^e			X			X		X
Research Biopsy ^e		X						X
Radiographic Assessments ^f		X ⁱ				X	Q3C	

- A. One treatment cycle is equal to 28 days
- B. Full physical exam is required at screening. Subsequent physical exams may be targeted.
- C. Refer to Laboratory Manual for details on correlative blood sample processing.
- D. Pathologic assessment to evaluate LOH score is a pre-screening requirement and will be performed on archival tissue or ctDNA. Sufficient tissue must also be available for whole exome sequencing in order to determine iHRD status.
- E. If archival metastatic tissue previously obtained is already available and suitable for research assessments, another metastatic biopsy will not be mandated. Research biopsy will only occur if considered safe and feasible by the treatment team. CBC with Differential, PT/INR and PTT will only be obtained in the pre-screening period if metastatic biopsy is planned.
- F. Radiographic assessments should include a CT chest/abdomen/pelvis and bone scan. PET/CT or MRI may be used as initial screening assessments.
- G. Assessments done during the screening period do not need to be repeated if within 7 days.
- H. Assessments do not need to be repeated if within 7 days
- I. Radiographic assessments do not need to be repeated if within 8 weeks

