4.4 End of study definition

The end of study is defined as the last expected visit/contact of the last patient undergoing the study. Follow up will continue for up to one year after the last patient discontinues treatment.

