5.11.1 Procedures for discontinuation of study treatment

The investigator should instruct the patient to contact the site before or at the time if Study treatment is stopped. A patient that decides to discontinue Study treatment will always be asked about the reason(s) and the presence of any AEs. The date of last intake of Study treatment should be documented in the CRF (electronic or paper). All Study treatment should be returned by the patient at their next on-site study visit or unscheduled visit. Patients permanently discontinuing Study treatment should be given locally available standard of care therapy, at the discretion of the Investigator.

Any patient discontinuing investigational product should be seen post discontinuation for the evaluations and sample collections outlined in the study schedule.

After discontinuation of the study medication at any point in the study, all ongoing AEs or SAEs must be followed until resolution unless, in the Investigator's opinion the condition is unlikely to resolve due to the patients underlying disease, or the patient is lost to follow up (see Section 5.12) All new AEs and SAEs occurring during the 30 calendar days after the last dose of study medication must be reported (if SAEs, they must be reported within 24 hours as described in Section 6.4.2) and followed to resolution as above. Patients should be seen within 30 days after discontinuing study medication to collect and / or complete AE information. For guidance on reporting adverse events after the 30 day follow up period see Section 6.4.2.1.

Discontinuation of Study treatment, for any reason, does not impact on the patient's participation in the study. The patient should continue attending subsequent study visits and data collection should continue according to the study protocol. If the patient does not agree to continue in-person study visits, a modified follow-up must be arranged to ensure the collection of endpoints

and safety information. This could be a telephone contact with the patient, a contact with a relative or treating physician, or information from medical records. The approach taken should be recorded in the medical records. A patient that agrees to modified follow-up is not considered to have withdrawn consent or to have withdrawn from the study.

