6. STUDY ASSESSMENTS AND PROCEDURES

Assessments will be performed according to the Schedule of Activities (SoA).

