6.2.2 Secondary and Exploratory Objectives

ORR and Radiographic Progression Free Survival

Radiographic assessments which include computed tomography scan of the chest, abdomen, and pelvis as well as a nuclear medicine bone scan will be conducted every 12 weeks (every 3 cycles) after screening. Radiographic response and progression will be defined per RECIST 1.1 criteria. RECIST 1.1 is an accepted methodology by regulatory authorities and will be used to assess tumor response in patients with soft tissue disease. For patients with bony disease, progression will be defined per PCWG3 criteria¹.

Exploratory Objectives

Correlative blood work and tissue analysis will be performed per the planned time points in the SoA. Full details of collection, processing, shipping, and storage of samples will be included in the Lab Manual.

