6.9 Statistical analyses

6.9.1 Efficacy analyses

Primary Objective

The primary objective is to determine the percentage of patients who are iHRD+ that achieve a PSA₅₀ response (i.e. $\geq 50\%$ decline in PSA from baseline). The lowest on treatment PSA will be defined as the lowest value following at least 12 weeks of treatment (i.e. the beginning of Cycle 4). The PSA₅₀ response rate will be calculated along with 90% confidence intervals (CI) using Wilson's method. PSA changes will be presented as waterfall plots per PCWG3 recommendations. If a patient drops out of the study prior to assessing best PSA response he will be considered as not having had a PSA₅₀ response.

ORR Response

For patients with measurable disease, ORR will be defined as a 30% decrease from baseline per RECIST 1.1 criteria at any time point. The percent of patients with ORR and 90% CI, calculated using Wilson's method, will be provided. Radiographic responses will be presented as waterfall plots.

rPFS, PSA PFS, OS

These endpoints are defined in section 3.5. The distributions of each endpoint will be estimated using the Kaplan-Meier method. Median times to event will be reported with 90% CIs using linear interpolation between steps of the survival curve.

Exploratory Objectives

Response rates and time to event endpoints as described above will be compared between patients who are iHRD+ and iHRD-. PSA and radiographic response rates including percentage and 90% CIs, calculated using Wilson's method, will be reported. Differences in response rates will be quantified using logistic regression with no additional adjustment. Time to event endpoints will be compared with log-rank tests.

If dropout is greater than anticipated, primary and secondary endpoint analyses will still be based on patients with 12 weeks of follow-up. However, the exploratory analysis will examine extreme scenarios in which endpoints for dropouts are imputed to minimize differences between iHRD+ and iHRD- patients.

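### Does the plan need a written rule for how exits at PSA or clinical progression enter radiographic PFS?

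*Combined protocol and SAP*

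**What the plan says.** Sections 1.2 and 4.1 let treatment run until radiographic, PSA or clinical progression, whichever is first, and add: "Patients will come off study at time of clinical, radiographic, or PSA progression". Before three cycles are complete, PSA progression alone is not a reason to stop.

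Section 5.11.1 says that stopping treatment for any reason leaves participation unchanged: "The patient should continue attending subsequent study visits and data collection should continue according to the study protocol". For patients who decline visits it requires a modified follow-up that secures the endpoints. Section 4.4 adds: "Follow up will continue for up to one year after the last patient discontinues treatment".

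On imaging, Section 6.2.2 sets CT and bone scans every 12 weeks after screening and says: "Radiographic response and progression will be defined per RECIST 1.1 criteria". Bone progression follows PCWG3 (Section 6.2.2 and Appendix E 2). Table 1 marks the row "Radiographic Assessments" at screening, Cycle 4 and every third cycle. The End of Treatment cell is blank and there is no later column.

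On analysis, Section 6.9.1 says of rPFS, PSA PFS and OS: "These endpoints are defined in section 3.5. The distributions of each endpoint will be estimated using the Kaplan-Meier method". Section 3.5 only names these endpoints.

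**The concern.** Treatment stops at the first of three kinds of progression, so some patients will stop without radiographic progression. If they also leave the study and are not scanned again, their rPFS time is unknown. Section 6.9.1 does not say what to do with them, and the definition it points to is absent. The time origin, the handling of deaths after such an exit, bone lesions still awaiting confirmation, and exits before the first scan at week 12 are also unwritten.

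The choice matters in principle. A patient with rising PSA or worsening symptoms is probably closer to radiographic progression than one without, so censoring would be informative and the curve too high. Counting the exit as an event would make the curve too low, because the earlier of two times cannot exceed either one. An ordinary confidence interval shows neither error.

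**Working it through.** **1. Does imaging stop?**

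| Points to stopping | Points to continuing |
|---|---|
| 1.2 and 4.1: patients come off study | 5.11: stopping treatment is not withdrawal; 5.11.1: visits and data collection continue and endpoints must be secured |
| Table 1: no scan at or after End of Treatment; Section 6 refers assessments to Table 1 | Table 1 has no post-treatment column at all, yet 4.4, 5.13 and 6.4.2.1 plan survival follow-up, so it does not list everything done after treatment |
| 6.2.2 counts scans in cycles | 6.2.2 sets no on-treatment limit, whereas 6.2.1 limits PSA to the treatment phase |

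Taken literally, leaving the study at progression would also end follow-up for overall survival, which is itself a secondary endpoint. Off treatment is the workable reading. The text remains ambiguous on scans, but does not show that they stop.

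**2. Could an exit count as an rPFS event?** Section 3.5 lists radiographic PFS and PSA PFS separately, and 6.2.2 with Appendix E 2 define progression for rPFS by imaging. Nothing supports counting a PSA or clinical exit as an rPFS event. Death is an event by the ordinary meaning of PFS, and 5.12 re-checks survival status to support PFS.

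**3. Size if scans stop and exits are censored.** The plan states no figure for rPFS. Its only power statement concerns PSA50. That one reproduces (8 or more responses in 20: power 0.868, one-sided error 0.0321, against 87% and 0.03) but does not bear on this point.

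Inputs: true median rPFS 5.8 months (the combined-cohort PFS quoted in 2.1, used here as an assumption) and scans every 12 weeks (6.2.2). Assumed, with no source in the documents: exponential times, median time to PSA progression 4-5.8 months, correlation 0.3-0.7, and, where included, clinical exits with median 12-24 months.

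True curve: S(t) = 2^(-t/5.8). 24 weeks = 24 × 7 / 30.44 = 5.52 months, so S = 2^(-0.952) = 0.517. At 48 weeks, 0.517² = 0.267.

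Simulated Kaplan-Meier with exits censored (400,000 patients per setting). The schedules differ because 4.1 and 6.2.1 measure PSA every cycle, while 1.2 and Table 1 measure it every third cycle.

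| PSA schedule | 24 weeks, no clinical exits | 24 weeks, with clinical exits | 48 weeks, no clinical exits |
|---|---|---|---|
| Every cycle, confirmed at next visit | 0.541-0.591 | 0.557-0.651 | 0.312-0.416 |
| Every third cycle, confirmed at 3 weeks | 0.535-0.575 | 0.553-0.634 | 0.307-0.389 |
| Every third cycle, confirmed at next scheduled visit | 0.516-0.519 | 0.535-0.590 | 0.287-0.311 |

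The 24-week shift runs from nil to 0.591 - 0.517 = 0.074 without clinical exits, and reaches 0.651 - 0.517 = 0.134 with them. At zero correlation with per-cycle PSA the estimate is 0.516-0.518, so there is no bias.

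**4. Against sampling error at n = 20, complete imaging.** At 24 weeks: 1.645 × √(0.517 × 0.483 / 20) = 1.645 × 0.112 = 0.184, or about 0.33-0.70; the simulated 5-95% range is 0.35-0.70. All the 24-week values lie inside it. At 48 weeks: 1.645 × √(0.267 × 0.733 / 20) = 0.163, against a largest tabulated shift of 0.416 - 0.267 = 0.149. For the median, the sampling range is 3.4-9.3 months. Censored medians without clinical exits are 5.9-8.1. With them, the highest value is 10.0 (per-cycle PSA), just outside; the other two schedules reach 9.2 and 7.5.

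**5. Would added bounds help?** With per-cycle PSA and no clinical exits, counting exits as events gives 0.280-0.419 at 24 weeks, and 1 minus the cumulative incidence gives 0.595-0.633: together about as wide as sampling error. At 48 weeks the upper bound is 0.480-0.562 against a true 0.267, further off than the censored estimate of 0.312-0.416.

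**The case for a change.** The strongest case for a change is that the reference to 3.5 leads nowhere, the trial is open-label, and the handling rule could be picked after the data are seen. Between censoring exits and counting them as events, the 24-week estimate moves by about 15-30 points with per-cycle PSA. The censoring shift is systematic, so its lying within sampling error does not remove it. Section 4.2 itself links PSA decline with tumour control, which supports the positive correlation. The exploratory log-rank comparison of iHRD+ with iHRD- patients inherits the gap.

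The faulty cross-reference, the unwritten censoring rule and the probable direction of the shift all stand. The 15-30 point contrast does not, because it needs a reading in which a PSA or clinical exit is a radiographic event, and the plan keeps those endpoints apart. What remains is the censoring shift, whose size cannot be derived from the documents. Exits before the first scan (5-10% in the illustration, or 1-2 of 20 patients) are partly covered: 6.9.1 bases the secondary analyses on patients with 12 weeks of follow-up if dropout exceeds expectation.

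**Conclusion.** No change is called for. This is a gap in wording that analysts fill sensibly: time from first dose to radiographic progression (RECIST 1.1 for soft tissue, PCWG3 for bone) or death, otherwise censored at the last evaluable scan. Writing that down would leave the main estimate, and any bias in it, as it is. Requiring scans after every such exit would add cost if they are not already done, and the extra bounds are too wide to sharpen the result.

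If scans do continue, as 5.11.1 suggests, neither bias arises. If they stop, rPFS at 24 weeks may be overstated by 0-7 points without clinical exits and by up to 13 points with them, under the assumed medians and correlations; independence gives zero. That lies within sampling error for 20 patients at 24 weeks, though the highest simulated median does not. rPFS carries no test or decision rule, and PSA50, on which the trial is sized, does not depend on it. A reader of the results should note how many patients stopped for PSA or clinical progression alone.
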